## **5 Handling of Missing Data**

Best efforts will be made to collect complete data for the clinical endpoints of interest, regardless of whether or not the subject received study drug/treatment. In order to minimize bias and take all randomised patients into the analysis when the proportion of missing data for a specific endpoint is larger than 1%, a multiple imputation analysis will be performed. Only endpoints listed in Sections 6.1 to 6.4, with the exception of the ECG endpoint Sum ST-segment deviation

resolution 30-min post-angiogram/PCI, will be imputed, if necessary. No imputation for the endpoints listed in Section 6.5 will be performed.

The baseline covariates age, sex, assigned treatment, body weight, infarct location (anterior or other), previous infarction, Killip class, heart rate, systolic blood pressure and time from symptom onset to randomisation, hypertension, diabetes, place of randomization, Q-wave, time of randomization (before or after protocol amendment 5), time of randomization to administration of tenecteplase or sheath insertion and type of access together with all single efficacy and safety endpoints, ECG (with the exception of the endpoint Sum ST-segment deviation resolution 30-min post-angiogram/PCI) and angiographic endpoints will be multiply imputed using the fully conditional specification (FCS) method using a regression or logistic regression model, whichever is applicable. Note that for the ECG endpoint successful reperfusion, the imputation will be done on the ST-segment resolution from which successful reperfusion will be determined. For mortality, the variables cardiac and non-cardiac mortality instead of overall mortality will be used. For non-intracranial bleeds, only the variables major and minor non-intracranial bleeds will be put in the model. Total non-intracranial bleeds will be determined later on. For stroke, the variables total stroke, will be put in the model. The subclassifications of ischaemic, intracranial haemorrhage, fatal, non-fatal, disabling, non-disabling will be done in a second phase in which the type will be imputed by a random draw from a binary distribution with a probability of success equal to the maximum of the observed event rate or 0.01 stratified by assigned treatment

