### **8.11 Subgroup Analyses**

Subgroup analyses will be done for the ECG efficacy endpoints and the combined clinical endpoint of 30-day total mortality, congestive heart failure, shock and recurrent myocardial infarction.

A test for interaction between subgroup and treatment group will be performed.

Subgroups:

Age	≤75 years; >75 years
Age	Quartiles of age
Time from symptoms onset to randomization	0–<1 hr; ≥1–<2 hr; ≥2 hr
Infarct location	Anterior; Inferior; Other
Sex	Male; Female
Systolic blood pressure	<100 mmHg; 100–139 mmHg; 140–159 mmHg; ≥160 mmHg
Killip class	I; II–IV
Hypertension	Yes; No
Diabetes	Yes; No
Weight	<60 kg; ≥60–90 kg; ≥90 kg
Place of randomization	Ambulance; community hospital
Q-wave	With/without new Q-waves (for index MI) at baseline
TIMI risk score	<5; ≥ 5
Period of randomization	Before protocol amendment 5; after protocol amendment 5
Type of access	Radial vs femoral

In case multiple infarct locations are present within one patient, the patient will be classified as anterior in case anterior is one of the locations or as inferior otherwise.

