***Table 16.1.2 Successful reperfusion by subgroups (FAS)***

Similar to 16.1.1

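### The imputation model in SAP 5 names no treatment-by-factor term, yet SAP 8.11 tests treatment-by-subgroup interaction on endpoints it imputes; if 8.11 uses the imputed data, a true interaction on ST resolution is diluted and the test is conservative

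*SAP*

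**What the plan says.** SAP 5 sets the trigger: "when the proportion of missing data for a specific endpoint is larger than 1%, a multiple imputation analysis will be performed". This covers the endpoints of SAP 6.1 to 6.4, "with the exception of the ECG endpoint Sum ST-segment deviation" resolution. Successful reperfusion (6.1.2) and aborted myocardial infarction (6.1.3) are therefore covered.

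The model is given as a list that begins "The baseline covariates age, sex, assigned treatment, body weight, infarct location (anterior or other), previous infarction, Killip class" and goes on to further baseline items and the other endpoints. All of these "will be multiply imputed using the fully conditional specification (FCS) method using a regression or logistic regression model, whichever is applicable". For reperfusion, "the imputation will be done on the ST-segment resolution from which successful reperfusion will be determined". The list contains no product of treatment with a baseline factor, and separate imputation by arm is not mentioned.

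SAP 8.11 then names 15 subgroup rows for the ECG endpoints and the 30-day composite, and states: "A test for interaction between subgroup and treatment group will be performed". Tables 16.1.2 and 16.1.3 apply this to successful reperfusion and aborted infarction. Section 8.11 does not say whether the tests use imputed or observed values, or on what scale.

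Two subgroup factors do not match the imputation model. Infarct location is imputed in two classes but analysed in three (anterior, inferior, other). TIMI risk score is a subgroup factor but is not a listed covariate.

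**The concern.** An imputation model should allow for the effects that the analysis will test. If treatment enters only as a main effect, every missing ST resolution is drawn as though the treatment effect were the same in all subgroups. A test for different effects is then run on data partly filled in under no difference.

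The trial is hypothesis-generating. The subgroup tables, for example by age, time from symptom onset and place of randomisation, are meant to suggest where the pharmaco-invasive strategy works better or worse. Dilution makes the tables look more consistent across subgroups than the observed ECGs would.

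**Working it through.** The plan states no missing-ECG rate, interaction size or interaction power, so there is no figure to reproduce. From the documents: 400 and 200 patients, reperfusion defined as ST resolution of at least 50%, imputation on the continuous scale, analysis by relative risk (RR). Everything else below is assumed: normal ST resolution with SD 30, the subgroup share, the cell means and the missing fractions.

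**1. Trigger.** 6/600 = 1.0% does not start imputation; 7/600 = 1.17% does.

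**2. Closed form on the ST-resolution scale.** Take a two-by-two layout (arm by subgroup) with n patients and missing fraction f in each cell, and w = n(1 − f) observed. Filling in from a main-effects fit shrinks the interaction by

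Σ(f/w) / Σ(1/w).

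If f is the same in all cells, this equals f exactly.

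**3. Worked example on the RR scale.** Subgroup share 25%. The cells are PPCI outside the subgroup (n = 150), PhI outside (300), PPCI inside (50) and PhI inside (100).

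- True means 65, 50, 50, 50: interaction 15 points. Success rates 0.691, 0.500, 0.500, 0.500. True log ratio of RRs = ln(0.500 × 0.691 / (0.500 × 0.500)) = 0.324.
- The additive fit moves each cell by 15 × (1/n)/Σ(1/n), giving means 62.5, 51.25, 57.5, 46.25 and success rates 0.662, 0.517, 0.599, 0.450.
- At 20% missing in every cell, the completed rates (0.8 × true + 0.2 × fitted) are 0.685, 0.503, 0.520, 0.490. Log ratio = 0.250. Attenuation = 1 − 0.250/0.324 = 23%.
- The same steps give 11% at 10% missing and 6% at 5%.

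Across the large-sample scenarios with a true interaction on ST resolution and no informative auxiliary variable, attenuation was 4.5-5.9%, 8.8-11.3% and 17.6-22.9% at 5%, 10% and 20% missing.

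**4. Departures from that rule.**

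- *Uneven missingness.* Subgroup share 20%, cells 320, 80, 160, 40; 8% missing in the first three and 25% in the last (PPCI, inside the subgroup). Then w = 294.4, 73.6, 147.2, 30.0. Overall missing = (560 × 0.08 + 40 × 0.25)/600 = 9.1%. Attenuation = (0.08 × 0.02378 + 0.25 × 0.03333)/0.05711 = 17.9%, which is 1.96 times the overall fraction. Other patterns went down to 0.61 times.
- *Informative auxiliary variables.* At 20% missing, a variable correlated with ST resolution at r = 0.4 gave attenuation of 15-19%, and at r = 0.7 gave 8-13%, so as little as 0.4 times the fraction.
- *Additive effects.* True means 80, 60, 65, 45 have no interaction on ST resolution, but the RRs differ: ln(0.434 × 0.841 / (0.631 × 0.691)) = −0.178. Simulated after imputation at 20% missing: −0.180. Nothing is lost.

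**5. Effect on the test.** 1,500 simulated trials of 400/200 with 20 imputations and an interaction of 15 points on ST resolution:

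| Missing | Mean log ratio of RRs, full data | Main-effects imputation | Power, main-effects imputation | Power, observed only | Type I error, main-effects imputation |
|---|---|---|---|---|---|
| 5% | −0.2725 | −0.2606 | 49% | 53% | 3.9% |
| 10% | −0.2816 | −0.2565 | 46% | 53% | 2.7% |
| 20% | −0.2824 | −0.2318 | 33% | 50% | 1.8% |

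Power with full data was 55-59%. With the treatment-by-subgroup term in the imputation model at 20% missing, the estimate was −0.283 against −0.284 with full data, and power was 49%. Type I error was then 2.7%, so the term removes the bias but the test stays somewhat conservative.

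**The case against.** The strongest reply is that two steps rest on silence. SAP 5 lists variables and does not exclude product terms, and 8.11 refers to neither 8.1 nor 8.5.1, where pooling over imputations is described. This stands as a limit on certainty. The natural reading still goes the other way. SAP 5 exempts only one ECG endpoint, keeps non-missing denominators for the endpoints it does not impute, and is otherwise detailed down to seeds and the order in which variables are dropped. An intended interaction term would be expected to appear.

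Second, Protocol 7.3 foresees no imputation at all. If the two documents were reconciled that way, the point would fall.

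Third, all tests are exploratory, no interaction test has stated power, and the distortion hides interactions without creating false ones. That is correct and limits the weight of the point.

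Fourth, the model contains other efficacy, safety and angiographic endpoints that may predict ST resolution and carry part of the interaction. This also stands, and is why attenuation can fall to about 0.4 times the missing fraction.

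A reader might infer that every interaction in the subgroup tables shrinks by the share of missing ECGs, or that this share is an upper bound. Neither is supported. Sum ST-deviation resolution is never imputed, an RR interaction that arises from additive effects is not attenuated, and uneven missingness can nearly double the pull. Nor do the documents show that ECG readings are often missing.

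**Conclusion.** The point holds conditionally. If 8.11 uses data imputed by the model as listed, the imputation is inconsistent with the interaction test: a true interaction on ST resolution is biased towards none and the test is conservative. At 2-5% missing ECGs the effect is small for an exploratory test. At 10-20% it is worth avoiding, and at 20% the simulated test does clearly worse on imputed data than on observed values alone.

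The sizes rest on assumed means, SD, subgroup share and missing fractions. They apply to successful reperfusion only. Aborted infarction, which also depends on cardiac markers, follows the same logic but has not been computed. For the 30-day composite at 1-3% missing the effect is negligible.

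It would go too far to say that the subgroup tables are biased as they stand, because that depends on a missing rate and a choice of data that the documents do not give.

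**What to change.** In SAP 5, impute ST-segment resolution separately by arm, or add treatment-by-factor terms for the 8.11 subgroup factors to its regression model. Enter those factors at their analysed levels, for example infarct location in three classes, and include TIMI risk score. In 8.11, state that the interaction tests use these imputations and add an observed-values analysis as a sensitivity check. Report missing ECGs by arm and subgroup, so that the reader can judge how much imputation contributes.

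The cost is a somewhat larger imputation model. If terms are added one factor at a time, it is extra runs of the 100 imputations for the factors tested. Using observed values alone would be simpler, but is not free: if missing ECGs depend on outcomes that the imputation model contains, that analysis discards information which imputation would use.

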### **8.12 Additional Analyses**

Kaplan-Meier curves will be created for the efficacy composite endpoint of primary interest and all cause death. The time to the first event (in days) will be used as time variable. In case no event is present, the last time the patient was seen will be used as censoring time.

CIF curves will be created for the other components of the efficacy composite endpoint of primary interest: shock, CHF and reinfarction. The time to the first event (in days) will be used as time variable, death will be the competing risk, the last time the patient was seen will be used as censoring time.

## 9 Analyses on the Pooled Elderly Sets

The analyses on the pooled elderly sets will be limited to the primary efficacy endpoints, all stroke endpoints and non-ICH bleeds.

### 9.1 Efficacy endpoints of primary interest

#### 9.1.1 Clinical endpoint

The results from STREAM 1 and 2 will be combined using the Mantel-Haenszel method. Assume that  $\hat{r}_h$  and  $\hat{V}_h$  are the point estimates of  $r_h = (\pi_{hA} \pi_{hB})$ , with  $\pi_{hA}$  and  $\pi_{hB}$  the event rates in both treatment groups, and its variance-covariance matrix in study h, where  $h = 1, 2$ . Define  $w_h = \frac{n_{hA}n_{hB}/n_h}{\sum_{h=1}^2 (n_{hA}n_{hB}/n_h)}$ ,  $h=1, 2$ , and then  $\hat{r} = \sum_{h=1}^2 w_h \hat{r}_h$  and  $V = \sum w_h^2 V_h$  with  $n_{hA}$  and  $n_{hB}$  the sample size in group A and B in study h, respectively, and  $n_h$  the total sample size in study h.

Assume that  $\hat{r} = \begin{pmatrix} \hat{r}_A \\ \hat{r}_B \end{pmatrix}$  and the relative risk can be estimated by  $\varphi = \frac{\hat{r}_A}{\hat{r}_B}$ .

The confidence intervals and the overall test are calculated after logarithmically transforming the relative risks ( $=\log(\varphi)$ ).

Denote by  $\hat{r}_t = (\log(\hat{r}_A) \quad \log(\hat{r}_B))'$  and  $V_t$  respectively the logarithmically transformed rates and the corresponding variance-covariance matrix.

Let  $s = (1 \quad -1)$  then  $Q = (s\hat{r}_t)'(sV_t s')^{-1}(s\hat{r}_t)$  is a test statistic which has approximately a chi-square distribution with 1 degree of freedom under the hypothesis  $H_0: \phi = 1$  (vs  $H_a$ : otherwise).

Let  $s = (1, -1)$ , the 95% confidence interval for the relative risk of treatment A versus B will be calculated by  $\exp(s\hat{r}_t \pm 1.96\sqrt{sV_t s'})$ .

#### 9.1.2 ECG based endpoints

##### 9.1.2.1 Successful reperfusion

Successful reperfusion will be analysed similarly as Section 9.1.1.

### **9.1.3 Combined ECG and clinical endpoints**

#### **9.1.3.1 Incidence of aborted myocardial infarction**

The incidence of aborted myocardial infarction will be analyzed similarly as described in 9.1.2.1.

#### **9.1.3.2 Need for rescue PCI/revascularization in Group A**

The Mantel-Haenszel weighted event rate (as described in Section 9.1.1) will be reported with a 95% confidence interval.

### **9.1.4 Angiographic endpoints**

#### **9.1.4.1 TIMI flow at first coronary angiography**

The TIMI flow at first coronary angiography will be compared between treatment groups by means of a stratified trend test, i.e. the VanElteren test in which is stratified on study. In addition, the combined numbers and percentages will be reported.

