The STREAM-1 trial^{15, 16} demonstrated that in STEMI patients presenting within 3 hours of symptom onset (who could not undergo PPCI within 60 minutes), a pharmaco-invasive strategy that includes tenecteplase, urgent PCI for failed reperfusion and angiography within 24 hours in the remaining fibrinolytic-treated patients, achieved a comparable 30-day composite endpoint of all-cause death, cardiogenic shock, congestive heart failure (CHF), and re-infarction when compared to timely, contemporary PPCI. Mortality was also similar in both treatment groups at 1 year.¹⁷ Importantly the original trial protocol was amended after 21% (n=379) of the intended enrolment because of an excess of intracranial haemorrhage (ICH) in patients ≥ 75 years. Thereafter there was a 50% reduction in the dose of tenecteplase in these patients. When concluded, the overall primary composite endpoint of death, cardiogenic shock, CHF and re-MI occurred in 12.4% of the PhI group versus 14.3% of the PPCI patients (relative risk (RR) 0.86; 95% confidence interval (CI) 0.68-1.09; P=0.21) in 1892 patients. Whereas no further ICH occurred in the subsequent 97 patients ≥ 75 years randomised to the PhI strategy, the relationship between the dose reduction and efficacy remains uncertain. Preliminary data indicates that the extent of ST-segment resolution 60 to 90 minutes after $\frac{1}{2}$ dose tenecteplase was comparable to full dose but this requires confirmation in a larger data set.¹⁸

Importantly at least one third of PhI- treated patients required urgent coronary intervention because of failed fibrinolysis or early recurrent ischemia after initially successful reperfusion.¹⁹ The role of

platelet aggregation as it relates to this issue is unclear, but has been postulated to be significant and is known to be ameliorated by administration of P2Y12 antagonists. In STREAM-1 no additional loading dose of clopidogrel was given because when designing the study no reliable data were available in patients ≥ 60 years. Hence the role of a more effective dosing of clopidogrel (a loading dose of 300 mg vs 75 mg used in STREAM-1) in patients ≥ 60 years is worthy of further exploration and will be incorporated in STREAM-2. Such a dose has been used safely in the elderly as reported by Larson et al.²⁰.

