4.1.2 Methods of assigning patients to treatment groups

Immediately after screening in the pre-hospital setting, eligible patients will be randomised 2:1 to the pharmaco-invasive therapy or to PPCI.

Randomisation will be performed centrally by means of an interactive voice response system (IVRS), which has to be called by the investigator or an authorised member of site staff.

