#### **9.1.4.2 TIMI flow at last coronary angiography**

TIMI flow at last coronary angiography will be analysed similarly as Section 9.1.4.1.

In case only one coronary angiography was performed, the TIMI flow measurement will be used for both the first and the last coronary angiography.

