**Table 24.2 Need for rescue PCI/revascularization in Pharmaco-invasive group (PES-P)**

**Table 25.1 Angiographic endpoints (PES-I)**

	Statistic	Randomised Treatment		P-value
		Pharmaco-Invasive	Primary PCI	
Patients Enrolled	N	xxx	xxx	
TIMI flow at first coronary angiography				X.XXX
TIMI 0	n/N (%)	xx/xxx (xxx.xx%)	xx/xxx (xxx.xx%)	
TIMI 1	n/N (%)	xx/xxx (xxx.xx%)	xx/xxx (xxx.xx%)	
TIMI 2	n/N (%)	xx/xxx (xxx.xx%)	xx/xxx (xxx.xx%)	
TIMI 3	n/N (%)	xx/xxx (xxx.xx%)	xx/xxx (xxx.xx%)	
TIMI flow at last coronary angiography				X.XXX
TIMI 0	n/N (%)	xx/xxx (xxx.xx%)	xx/xxx (xxx.xx%)	
TIMI 1	n/N (%)	xx/xxx (xxx.xx%)	xx/xxx (xxx.xx%)	
TIMI 2	n/N (%)	xx/xxx (xxx.xx%)	xx/xxx (xxx.xx%)	
TIMI 3	n/N (%)	xx/xxx (xxx.xx%)	xx/xxx (xxx.xx%)	

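### Pooled elderly TIMI flow has a study-stratified test, but its percentages read as crude sums over two trials. They can carry a small false arm difference if STREAM-1 was not 2:1 and flow differs between trials.

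*SAP*

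**What the plan says.** The pooled elderly sets (SAP section 4) join patients aged 75 or over from STREAM-2 with those from STREAM-1 randomised after its amendment 2.

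For TIMI flow at first angiography, SAP 9.1.4.1 compares the arms by a "stratified trend test, i.e. the VanElteren test in which is stratified on study" and continues: "In addition, the combined numbers and percentages will be reported". Section 9.1.4.2 carries this over: "TIMI flow at last coronary angiography will be analysed similarly as Section 9.1.4.1". Table 25.1 has one n/N (%) cell per arm and TIMI grade and one p-value, with no rows by study and no weighted rate. Table 25.2 is a title only.

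Other pooled endpoints are handled differently. SAP 9.1.1 states "The results from STREAM 1 and 2 will be combined using the Mantel-Haenszel method" and applies the same study weight to both arms. Sections 9.1.2, 9.1.3.1 and 9.2 follow it, and 9.1.3.2 asks for a Mantel-Haenszel weighted rate even for the single-arm rescue endpoint.

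In STREAM-2, "eligible patients will be randomised 2:1 to the pharmaco-invasive therapy or to PPCI" (Protocol 4.1.2). Neither document gives the STREAM-1 ratio.

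**The concern.** If the two trials used different allocation ratios, STREAM-1 makes up a different share of the PhI column than of the PPCI column. A difference in TIMI flow between the trials that affects both arms alike then shows up as a difference between arms.

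The stratified p-value does not test that crude difference, and no relative risk or other estimate is planned for pooled TIMI flow. A reader who wants the size of the effect has only the crude percentages. The pooled sets exist to firm up the estimates in the elderly, so these percentages are likely to be quoted.

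**Working it through.** The plan gives no pooled TIMI figure to reproduce, so the check asks how large a false difference could be.

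**Inputs**
- STREAM-2 allocation is 2:1 (Protocol 4.1.2).
- STREAM-1 PhI patients aged 75 or over after the dose amendment: 97. Protocol 1.1 says "no further ICH occurred in the subsequent 97 patients" of that age in the PhI arm. I take this to be the amendment named in SAP section 4.
- STREAM-1 PPCI patients of that age: not given. Assumed 97 (1:1) or 48.5 (2:1).
- STREAM-2 PhI patients aged 75 or over: not given; the only floor is about 100 PhI patients aged 70 or over. Assumed 50 to 200, with half as many PPCI.
- TIMI rates: none given. Assumed trial differences are 5, 10 and 20 points.

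**Can the STREAM-1 ratio be inferred?** Protocol 1.1 reports 12.4% v 14.3%, RR 0.86 (0.68-1.09), P=0.21, in 1892 patients. The standard error of log RR is sqrt[(1-pA)/(nA pA) + (1-pB)/(nB pB)].
- 1:1: SE 0.1175, CI 0.683-1.083, p=0.20.
- 2:1: SE 0.1229, CI 0.676-1.094, p=0.22.

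Both are close to the reported result, so the ratio stays open.

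**Formula.** Let s be the STREAM-1 share of an arm, and p1 and p2 the TIMI 3 rates in STREAM-1 and STREAM-2, equal across arms within each trial. The crude arm rate is s·p1 + (1-s)·p2, so

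false difference (PhI minus PPCI) = (s_PPCI - s_PhI) × (p2 - p1).

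If there is a true difference d, the same in both trials, the crude difference is d plus this term.

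**Worked case.** STREAM-1 97 v 97, STREAM-2 100 v 50, TIMI 3 50% in STREAM-1 and 60% in STREAM-2.
- s_PhI = 97/197 = 49.2%; s_PPCI = 97/147 = 66.0%; gap 16.7 points.
- Crude: PhI 55.1%, PPCI 53.4%, a false difference of 1.7 points.
- Weights of 9.1.1: 97×97/194 = 48.5 and 100×50/150 = 33.3, so STREAM-1 gets 48.5/81.8 = 0.593. The weighted rate is 0.593×50 + 0.407×60 = 54.1% in both arms, a difference of 0.

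**Range with STREAM-1 at 1:1**

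| STREAM-2 PhI | STREAM-1 share of PhI | of PPCI | Gap | False difference at 5 / 10 / 20 points |
|---|---|---|---|---|
| 50 | 66.0% | 79.5% | 13.5 | 0.7 / 1.4 / 2.7 |
| 100 | 49.2% | 66.0% | 16.7 | 0.8 / 1.7 / 3.4 |
| 137 | 41.5% | 58.6% | 17.2 (maximum) | 0.9 / 1.7 / 3.4 |
| 200 | 32.7% | 49.2% | 16.6 | 0.8 / 1.7 / 3.3 |

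With STREAM-1 at 2:1, the shares are equal in every row and the false difference is 0, apart from chance imbalance. It is also 0 if p1 = p2.

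**Is the p-value safe?** I simulated 4000 null data sets at 97/97 and 100/50. The van Elteren test rejected 4.7%, 4.9% and 5.1% of the time at trial differences of 0, 10 and 20 points. An unstratified rank test rejected 4.5%, 6.3% and 9.8%. The planned test keeps its level.

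**The case against.** The strongest reply is that nothing inferential is exposed. The TIMI test is stratified, the binary endpoints are Mantel-Haenszel weighted, and the percentages are descriptive in a hypothesis-generating trial. Table 1 prints the pooled-set size by study and arm, so an unequal mix will be visible. All of this stands and limits the point to presentation.

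The size is also small against sampling error. In the worked case the 95% half-width at 54% is 1.96 × sqrt[0.54×0.46×(1/197 + 1/147)] = 10.6 points, against 1.7. This stands too, although a known bias with a trivial remedy need not be left in.

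The word used for the percentages might be meant in the Mantel-Haenszel sense. The shells do not settle it: Table 24.1 also shows n/N (%) although 9.1.3.2 requires a weighted rate. At the least the wording needs clarifying.

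A reader might point to the clopidogrel loading dose as the source of a trial difference. That does not fit. The loading dose is new in the PhI arm only (Protocol 1.1), while PPCI antiplatelet treatment follows local practice (Protocol 4.1.4.2). A change in one arm is a difference in treatment effect between trials, not the common shift needed here. A change in PCI practice between the two trial periods would qualify, but the documents give no figure for it.

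**Conclusion.** The point holds as a minor, conditional reporting weakness confined to the pooled TIMI percentages. A false arm difference needs both a STREAM-1 ratio other than 2:1 and a between-trial difference in TIMI flow common to both arms. Neither can be confirmed from the documents. With STREAM-1 at 1:1 and 97 per arm, the false difference is at most about 17% of the between-trial difference; if either condition fails, it is zero.

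Two stronger inferences are tempting. One is that the pooled elderly comparison as a whole is confounded. The documents do not support this, because the TIMI test is stratified on study and the relative risks of 9.1.1 and 9.2 use common study weights. The other is that the crude percentages beside the relative risks in Tables 23.1 and 26.1 must be replaced. There the Mantel-Haenszel relative risk already carries the effect, and showing raw n/N next to it is a matter of display.

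**What to change.** In SAP 9.1.4.1 and 9.1.4.2 and in Tables 25.1 and 25.2:
- report TIMI counts and percentages by study and arm;
- give the pooled percentage in each TIMI category weighted by the w_h of 9.1.1, with the same weights in both arms, in line with 9.1.3.2 for rescue PCI;
- add a footnote that the weighted percentages do not equal the pooled n/N.

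Keep the van Elteren test as it is, and leave the n/N (%) display in Tables 23.1 and 26.1 unchanged. The cost is a sentence in the SAP, a few lines of programming with weights already defined, some extra table rows and the footnote.
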